4.3.1 Allocation to Treatment

This is an open-label study; therefore, blinding is not applicable.

In the dose-escalation portion (Stage 1), withdrawals occurring prior to completion of the DLT period will be replaced so as to ensure that a full cohort is available at the time of CRC review. Replacement patients can only be made for those who discontinue for reasons other than safety.

In the expansion portion (Stage 2), 20 patients will be randomized in a 1:1 ratio to receive GDC-0084 at the RP2D for QD dosing, under either fed or fasted conditions on Days 1 and C2D1. Details of the fed/fasted instructions are provided in section 4.4.1. of this protocol.

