Protocol Number: NVGN-0084-201 Version: Amendment 4 IND Number: 112,608

Dose-Escalation Rules

Dose-escalation will occur in Stage 1:

The initial dose (Dose Level 0) for QD MTD determination in will be 60 mg. Dose levels will increase in 15 mg steps:

- The dose-escalation portion of the study (Stage 1) will use a "3 + 3" design to assess the safety, tolerability, and PK of GDC 0084 administered orally in 28-day cycles:
- Each dose cohort will initially enroll 3 patients. If none of these patients experiences a DLT within the DLT assessment period (Day 1 - 28), escalation will proceed to the next higher dose level by opening the next higher dose cohort with newly recruited patients;
- If 1 patient experiences a DLT, the cohort will be expanded until a second patient experiences a DLT or to a maximum of 6 patients. When a second patient has a DLT, the MTD is determined as 1 dose level below the current dose level; i.e. the highest dose level at which less than 1/3 of patients (e.g. 1 of 6) experiences a DLT will be declared the MTD.
- If 2 or more patients experience a DLT at Dose Level 0, the MTD will be declared at 45 mg, which was the MTD established in the previous phase I study in patients with advanced glioma with a QD dosing schedule.

On the basis of the review of real-time safety data and available preliminary PK data from this study with GDC-0084, dose-escalation may be halted or modified by the sponsor as deemed appropriate.

Decisions regarding dose-escalation and selection will be made by a CRC including the medical monitor, recruiting Investigators, sponsor representative and any other relevant and necessary expert on as needs basis, according to the CRC charter.

Definition of Dose Limiting Toxicity

All AEs, including DLTs, will be reported, with severity assessed according to National Cancer Institute (NCI) Common Terminology Criteria for Adverse Events (CTCAE), version 4.03. In case a patient experiences one of the below, study participation will be terminated for this patient and the EoT visit should be performed.

For dose-escalation purposes, DLT assessments will be performed by the sponsor in consultation with the Investigators during the CRC meetings.

A DLT is defined as any one of the following toxicities occurring within the DLT assessment window (Cycle 1, Days 1 - 28) and assessed by the Investigator to be probably or possibly related to GDC-0084:

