- Grade ≥ 3 non-hematologic or non-hepatic toxicity that is not related to hyperglycemia or hyperlipidemia or mucositis/stomatitis and is not due to disease progression or another clearly identifiable cause, excluding the following:
 - Alopecia of any grade;
 - Grade 3 fever or Grade 4 fever < 5 days duration;
 - Grade 3 infection < 5 days duration or that responds to treatment;
 - Grade 3 weight gain or loss;
 - Grade 3 diarrhea lasting less than 5 days or that responds to standard-of-care therapy including hospitalization;
 - Grade 3 nausea or vomiting, in the absence of premedication, that lasts for less than 48 hours or responds to standard-of-care therapy:
 - Grade 3 or asymptomatic Grade 4 electrolyte imbalance that resolves or improves within 7 days with or without medical intervention, including hospitalization;
 - Grade 3 or 4 serum amylase or lipase or creatine phosphokinase laboratory abnormality that is asymptomatic (without other laboratory evidence suggestive of pancreatitis, rhabdomyolysis, or other major organ dysfunction) and returns to baseline within 7 days of interrupting study drug;

Version: Amendment 4 Date: 31 Mar 2020

Protocol Number: NVGN-0084-201 IND Number: 112.608

o Grade ≥ 3 total bilirubin or hepatic transaminase (aspartate aminotransferase [AST] and alanine aminotransferase [ALT]) elevations that return to ≤ Grade 1 (if normal at study entry) or ≤ baseline values within 7 days of interrupting study drug:

- Note: Allergic reactions that necessitate discontinuation of study drug will not be considered a DLT:
- Grade ≥ 3 symptomatic fasting hyperglycemia (e.g., dehydration or acidosis requiring hospitalization):
- Grade ≥ 4 fasting hypercholesterolemia or triglyceridemia for ≥ 14 days despite intervention with a lipid-lowering agent;
- Grade ≥ 4 thrombocytopenia;
- Grade 3 thrombocytopenia that lasts ≥ 7 days or is associated with clinically significant
- Grade ≥ 4 neutropenia (absolute neutrophil count < 500/µL) lasting ≥ 7 days or accompanied by fever (oral or tympanic temperature ≥ 38.0°C [100°F]);
- Grade ≥ 3 total bilirubin or hepatic transaminase (ALT or AST) elevations that do not return to ≤ Grade 1 (if normal at study entry) or ≤ baseline values within 7 days of interrupting study drug:
- For patients with Gilbert's disease and with Grade 2 bilirubin at baseline, total bilirubin ≥ 10 x upper limit of normal (ULN) will be considered a DLT;
- Bradycardia Grade ≥ 2;
- Myocardial ischemia Grade ≥ 2;

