4.11 Criteria for Removal from Study

4.11.1 Removal of Patients

Patients will be advised in the Informed Consent Form (ICF) that they have the right to withdraw from the study at any time without prejudice, and may be withdrawn at the Investigator's, the contract research organization's (CRO's) or Kazia Therapeutics Limited's discretion at any time. If a patient

Version: Amendment 4 Date: 31 Mar 2020

Protocol Number: NVGN-0084-201

IND Number: 112.608

drops out of the study or is withdrawn from the study, the withdrawal form in the patient's CRF should be completed and all study drug supplies should be retrieved. On the withdrawal page the Investigator should record the date of the withdrawal, the person who initiated withdrawal and the reason for withdrawal.

Reasonable effort should be made to contact any patient lost to follow up during the course of the study in order to complete assessments and retrieve any outstanding data and study medication/supplies.

The following are reasons for patient withdrawal:

Withdrawn by the Investigator due to:

- Protocol deviation (e.g. dosing regimen, failure to comply with clinic visit schedule);
- · Administration of an excluded medication;
- Co-existing disease;
- Worsening of condition;
- Pregnancy;
- Clinically significant abnormal laboratory value(s).

The patient requested withdrawal due to:

- An AE for which the Investigator did not consider removal from the study necessary;
- Perceived insufficient therapeutic effect:
- Co-existing disease:
- Withdrawal of consent.

Other reasons for withdrawal may include:

- Patient died;
- Kazia Therapeutics Limited/CRO request the patient to be withdrawn;
- Lost to follow-up;
- Administrative problems.

Withdrawals will only be replaced in the dose finding/MTD portion (Stage 1) of the phase 2a study to ensure that a full cohort is available at the time of CRC review.

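### Section 4.3.1 bars replacing a Stage 1 patient who stops for safety without a DLT, so a cohort can meet the written 3+3 escalation rule on two fully exposed patients unless the CRC or sponsor steps in

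*Combined protocol and SAP*

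**What the plan says.** **Replacement.** Section 4.3.1 states that in Stage 1 "withdrawals occurring prior to completion of the DLT period will be replaced so as to ensure that a full cohort is available" when the CRC meets. The next sentence restricts this: "Replacement patients can only be made for those who discontinue for reasons other than safety". It does not separate a safety stop that is a DLT from one that is not.

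Section 4.11.1 covers the same ground without the restriction: "Withdrawals will only be replaced in the dose finding/MTD portion (Stage 1", again so that the CRC has a full cohort.

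**DLT definition.** Section 3.7.1 names one safety stop that is not a DLT: "Allergic reactions that necessitate discontinuation of study drug will not be considered a DLT". A DLT normally ends participation, although the same section allows continued dosing after a reversible one if the Investigator and medical monitor agree.

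**Escalation.** Under Section 3.7.1 each cohort starts with three patients. If none has a DLT in Days 1–28, "escalation will proceed to the next higher dose level by opening the next higher dose cohort with newly recruited patients". One DLT expands the cohort to at most six; a second DLT sets the MTD one level lower. No minimum exposure or completion of Day 28 is required, and Section 6.3.1 defines no DLT-evaluable population.

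**Discretion.** The CRC takes dose decisions under its charter, and "dose-escalation may be halted or modified by the sponsor as deemed appropriate". The synopsis gives three patients per cohort as a minimum.

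**The concern.** A 3+3 decision reads each patient without a DLT as evidence that a 28-day cycle is tolerable. A patient who stops after a few days supplies little of that evidence but still counts as DLT-free.

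Take a cohort of three in which one patient has an allergic reaction on Day 4 and stops, and no DLT occurs in the other two. The patient has had no DLT, Section 4.3.1 forbids a replacement, and the escalation condition is met on two fully exposed patients.

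Under the written rule this error can only favor escalation. DLTs are the primary endpoint, the 60 mg start is above the 45 mg MTD of the phase 1 study, and the selected dose goes on to 20 patients in Stage 2. The difference between Sections 4.3.1 and 4.11.1 also leaves a site unsure whether to replace such a patient.

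**Working it through.** **The plan's own figures.** The protocol states no operating characteristics for the 3+3 rule. Its sample sizes reproduce: four named dose levels × 6 = 24 at most in Stage 1; adding 20 for Stage 2 to 6, 12 and 24 gives 26, 32 and 44. This point does not dispute them.

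**Inputs.** From Section 3.7.1: three patients first, three more after one DLT, escalation on 0/3 or 1/6, and an MTD threshold below 1/3. The documents give no true DLT rate for these dose levels and no rate of non-DLT safety stops. Assumed values:

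- *p*, the true DLT rate: 1/3 (the protocol's threshold), 0.40 and 0.50; *q* = 1 − *p*.
- *s*, the chance per patient of a non-DLT safety stop in Cycle 1: 2%, 5% and 10%.
- *c*, the share of DLT risk that a stopped patient still carries: 0 (uninformative, the upper end) or 0.5.

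**1. Full exposure.** P(escalate) = *q*³ + 3*pq*² × *q*³. At *p* = 1/3: 0.296 + 0.444 × 0.296 = 0.428.

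**2. Given one stop among the first three.** P = (1 − *cp*)*q*² + [*cp* × *q*² + (1 − *cp*) × 2*pq*] × *q*³. At *p* = 1/3:

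- *c* = 0: 0.444 + 0.444 × 0.296 = 0.576.
- *c* = 0.5: 0.370 + 0.444 × 0.296 = 0.502.

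| True DLT rate | Full exposure | One stop, *c* = 0.5 | One stop, *c* = 0 |
|---|---|---|---|
| 1/3 | 0.428 | 0.502 | 0.576 |
| 0.40 | 0.309 | 0.386 | 0.464 |
| 0.50 | 0.172 | 0.242 | 0.312 |

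The rise is 7 to 15 points. After no DLTs, the one-sided 95% upper bound on the DLT rate is 1 − 0.05^(1/3) = 63% for 0/3 and 1 − 0.05^(1/2) = 78% for 0/2.

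**3. How often.** The chance of at least one stop in three patients is 1 − (1 − *s*)³: 6%, 14% and 27% at *s* = 2%, 5% and 10%.

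**4. Averaged over all cohorts.** Put *p*′ = *p*(1 − *s*(1 − *c*)) into the formula in step 1. At *p* = 1/3, against 0.428:

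| *s* | *c* = 0.5 | *c* = 0 |
|---|---|---|
| 2% | 0.434 | 0.441 |
| 5% | 0.444 | 0.461 |
| 10% | 0.461 | 0.494 |

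The rise runs from 0.6 to 6.6 points. At *p* = 0.40 and 0.50 the largest rises are 6.9 points (0.309 to 0.378) and 6.2 points (0.172 to 0.234).

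**5. If the CRC acts.** Steps 2 and 4 assume that the CRC applies the written rule and nothing else. Suppose instead that it holds escalation at the second non-DLT stop in a cohort, still with no replacement. Enumerating all outcomes at *p* = 1/3 gives:

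| *s* | *c* = 0.5 | *c* = 0 |
|---|---|---|
| 2% | 0.433 | 0.439 |
| 5% | 0.436 | 0.449 |
| 10% | 0.431 | 0.452 |

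With *c* = 0 the excess over 0.428 falls from 6.6 to 2.4 points at *s* = 10%, and from 3.3 to 2.1 at 5%. At 2% there is little to remove (1.3 to 1.1). A CRC that adds a fully exposed patient for every such stop returns the cohort to 0.428.

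**6. Cost of replacing.** Extra patients for a 12-patient Stage 1 = 12*s*/(1 − *s*): 0.24, 0.63 and 1.33. Delay per replacement: up to 28 days of screening plus a 28-day DLT period, so up to about 56 days.

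**The case against.** The strongest reply is that escalation is not mechanical. The CRC decides with real-time safety data, the sponsor may halt or modify escalation, and Section 4.3.1 itself aims at a full cohort for CRC review. AEs are collected for 28 days after the last dose, so the CRC would know of the short exposure. It could also add a fourth patient, because the synopsis sets only a minimum of three. All of this stands, and it is why the point is minor. What remains is that these steps are discretionary, while the written bar points the other way.

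It can also be said that the bar stops toxic patients from being swapped out. That aim is sound, but it needs the bar only for patients with a DLT, together with CRC sight of the other safety stops.

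Three stronger readings are tempting, and the documents do not support them:

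- *Escalation on two patients will follow.* The text shows only that the rule can be met that way; the CRC or sponsor can prevent it.
- *Any evaluability rule in the CRC charter would contradict the protocol.* The charter is not among the documents. A charter rule requiring three evaluable patients could be met by enrolling a fourth.
- *Patient-requested withdrawal is a second certain route.* Section 4.11.1 lists "An AE for which the Investigator did not consider removal from the study necessary" among the patient's reasons. Whether that is a safety reason under Section 4.3.1 is undefined, and that such an AE would not be a DLT is inference, since patients may continue after a reversible DLT. The allergic reaction is the express case, and known hypersensitivity to the excipients or to other PI3K/mTOR inhibitors is an exclusion criterion.

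**Conclusion.** The gap is real but minor. A stated rule, not just a missing detail, lets an under-exposed patient count as DLT-free without replacement, and two sections of the protocol differ on replacement.

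At a true DLT rate of 1/3, the chance of escalating is 43% with full exposure and 50–58% given one non-DLT safety stop among the first three. Averaged over assumed stop rates of 2–10%, it rises by about 1 to 7 points. The top of that range needs both a 10% stop rate and a stopped patient who tells us nothing. These figures take the CRC to follow the written rule without using its discretion; CRC action would remove much of the excess.

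**What to change.** - Replace the second sentence of Section 4.3.1 with: *Patients who have a DLT will not be replaced; a patient who discontinues before completing the DLT period without a DLT, for any reason, will be replaced.*
- Require at least three DLT-evaluable patients before escalation, and up to six on expansion unless a second DLT occurs first. DLT-evaluable means that the patient had a DLT or completed the DLT period.
- Report every non-DLT safety stop to the CRC before it decides, so that replacement does not hide a poorly tolerated dose.
- Align Section 4.11.1.

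The cost is a few sentences; about 0.2, 0.6 or 1.3 extra patients for a 12-patient Stage 1 at assumed stop rates of 2%, 5% or 10%; and up to about 56 days for each replacement.

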4.4 Study Interventions

4.4.1 **Treatment Schedule**

Prior to Screening

Version: Amendment 4 Date: 31 Mar 2020

Protocol Number: NVGN-0084-201 IND Number: 112.608

All patients will receive concomitant XRT/TMZ or XRT delivered as fractionated focal irradiation in daily fractions of 2 Gy given 5 days per week for 6 weeks, for a total of 60 Gy, with concomitant administration of daily oral TMZ 75 mg/m²/day from the first day to the last day of radiotherapy.

Patients must have recovered from side effects of this therapy to at least baseline or Grade 1 before entering the study. Lymphopenia and/or alopecia may be Grade 2 if clinically indicated in the judgement of the investigator.

After Screening/Enrollment

After screening, in Stage 1, the initial cohort will receive an oral dose of 60 mg GDC-0084 QD (4 x 15 mg capsules). Patients of future cohorts are planned to receive GDC-0084 at increasing levels with 15 mg steps according to the dose-escalation rules until disease progression or an unacceptable toxicity, whichever occurs first.

For the Stage 2 expansion, patients will receive doses of oral GDC-0084 at the RP2D established from Stage 1 for QD dosing in 28-day cycle until disease progression or an unacceptable toxicity, whichever occurs first.

Fed and Fasted Instructions

Days	C1D1 and C2D1 only	All other days
	(i.e. just 2 days in total)	
Fed Arm	On days C1D1 and C2D1 ONLY, patients allocated to the fed arm should consume a high-fat, high-calorie meal approximately 30 minutes prior to dosing , and should then refrain from eating for at least 4 hours post-dose. The high-fat (approximately 50 percent of total caloric content of the meal) and high-calorie (approximately 800 to 1000 calories) meal should derive approximately 150, 250, and 500-600 calories from protein, carbohydrate, and fat, respectively.	Patient can follow their own normal diet, which ideally should remain as consistent as possible,
	Example of the meal is two eggs fried in butter, two strips of bacon, two slices of toast with butter, four ounces of hash brown potatoes and eight ounces of whole milk. Alternatively, for vegetarians, beans, peas, tofu and cheese are good sources of protein and fat that satisfy protocol criteria.	and; Capsules must be taken 1 hour before food or 2 hours after food, as stated in Diary.
Fasted Arm	On Days C1D1 and C2D1, those patients allocated to the fasted arm should have fasted overnight for at least 10 hours, and should continue to fast for at least 4 hours post-dose. Water may be consumed as required, except for the period one hour before dosing to one hour post-dosing.	As above.

4.4.2 **Schedule of Assessments**

Screening evaluations are to be conducted within 28 days prior to start of protocol-directed therapy. Scans must be done within 14 days prior to the start of therapy. If the patient's condition is deteriorating during the 28-day screening period, laboratory evaluations should be repeated within 24 hours prior to initiation of the first cycle of therapy. Timing of assessments is given in Table 1 below. Details of assessments are outlined in Section 4.6.

Sponsor: Kazia Therapeutics Limited Version: Amendment 4 Date: 31 Mar 2020

Protocol Number: NVGN-0084-201

IND Number: 112,608

Table 1: Schedule of Assessments – Stage 1 and Stage 2

	Screening Day -28 to -1	Cycle 1 Enrollment / Week 1 Day 1	Cycle 2 Day 1	Repeat Cycle 2 Assessments for Cycle 3 and onwards			[
				Every 4 Weeks	Every 8 Weeks	End of Treatment Visit	Short-Term Follow-up Visit	Long term Follow-up Visits ^k
Visit Window			+/- 3 days	+/- 3 days	+/- 3 days	Within 7 days	28 days from last dose +/- 3 days	+/- 14 days
Informed Consent	Х							
MGMT Promoter Status ^a	Х							
Demographics	Х							
Medical/Cancer History	Х							
Physical Examination	Х	Х	Х	Х		Х	Х	
Ophthalmologic Examination ^b	Х				Х			
Urine Test for protein ^c	Х							
Vital Signs	Х	Х	Х	Х		Х	Х	
Weight	Х	Х	Х	Х		Х	Х	
Height	Х							
KPS	Х	Х	Х	Х		Х	Х	
MRI ^d		Х			Х	Х		
FDG-PET scane		Х			Ī			
ECG ^f	Х	Х	Х	Х		Х	Х	
LVEF (ECHO or MUGA)	Х				Х			

Version: Amendment 4 Date: 31 Mar 2020 Protocol Number: NVGN-0084-201

IND Number: 112.608

		Cycle 1	Cycle 2		Cycle 2 ts for Cycle nwards			
	Screening Day -28 to -1	Enrollment / Week 1 Day 1	Day 1	Every 4 Weeks	Every 8 Weeks	End of Treatment Visit	Short-Term Follow-up Visit	Long term Follow-up Visits ^k
Visit Window			+/- 3 days	+/- 3 days	+/- 3 days	Within 7 days	28 days from last dose +/- 3 days	+/- 14 days
aPTT/PT/INR	Х	Х	Х	Х		Х		
bHCG Pregnancy Test ^g	Х	Х	Х	Х		Х		
PK Sampling ^h		Х	Х					
Hematology, Chemistryi	Х	Х	Х	Х		Х	Х	
GDC-0084 Administration ^j		Х	Х	Х				
Study Drug Compliance			Х	Х		Х		
Concomitant Medications/Procedures	Х	Х	Х	Х		Х	Х	
AEs	Х	Х	Х	Х		Х	Х	
Disease status (including PFS and OS)								Х
Disease related therapies								Х

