3.7 Study Design

This phase 2a study consists of an open-label, multicenter dose-escalation study with expansion, designed to assess the safety, tolerability, MTD, PK and clinical activity of GDC-0084 in patients with newly-diagnosed GBM (WHO Grade IV astrocytoma) with unmethylated MGMT promoter status.

The MGMT promoter status must be confirmed by validated polymerase chain reaction (PCR) or validated alternative genomic analysis. Eligible patients must have undergone surgical resection of the tumor(s) and initial treatment with XRT/TMZ (Stupp regimen).

The maximum overall duration of the study is estimated to be 2 years. This study will comprise 2 stages, Stage 1 (dose-escalation) and Stage 2 (dose expansion and fed/fasted investigation)..

Stage 1 (dose-escalation) will enroll approximately 12 patients (range: 6 - 24 patients; i.e. up to 6 patients at 60 mg, at 75 mg, at 90 mg, at 105 mg....) for determination of the QD MTD.

Stage 2 (dose expansion) will enroll 20 patients, who will receive GDC-0084 QD at the MTD established for QD dosing in Stage 1. Patients in Stage 2 will be randomized in a 1:1 ratio to either receive the drug under fasted conditions or under fed conditions.

Protocol Number: NVGN-0084-201 Version: Amendment 4 IND Number: 112,608 Date: 31 Mar 2020

The total sample size for the study is approximately 32 patients (range: 26 - 44 patients).

3.7.1 Stage 1

[figure not shown]
Dose-Escalation and Maximum Tolerated Dose

GDC-0084 administration will occur in 28-day cycles to investigate whether it is possible to increase the previously established MTD of 45 mg QD relating to Phase 1 patients with progressive or recurrent high-grade gliomas. Starting dose will be 60 mg QD, subsequently escalating in 15 mg increments until the MTD is reached. PK will be evaluated from the initial 60 mg dose level (Dose Level 0) onwards. If the QD MTD cannot be escalated above 45 mg, then it will revert to 45 mg QD, which is the MTD established in an earlier phase 1 study. A standard "3 + 3" design will be adopted. A minimum of 3 patients will be enrolled, even if the MTD is confirmed as 45 mg. During Cycle 1 (Days 2 to Day 28) all doses are to be administered at least 1 hour before or 2 hours after food to ensure the study medication is taken on an empty stomach.

Figure 1 provides a study diagram.

Version: Amendment 4 Date: 31 Mar 2020

Figure 1: Study Diagram

Protocol Number: NVGN-0084-201

IND Number: 112,608

Date: 31 Mar 2020

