5.2 Reporting Period

For AEs, the active reporting period to Kazia Therapeutics Limited or its designated representative begins from the time that the patient provides informed consent, which is obtained prior to the patient's participation in the study, i.e., prior to undergoing any study-related procedure and/or receiving investigational product, through and including 28 calendar days after the last administration of the investigational product, including administration during long term treatment.

Additionally, all SAEs brought to the attention of the Investigator during the period starting from the time the patient signed the ICF and ending not earlier than 28 days following administration of the last

Date: 31 Mar 2020

Protocol Number: NVGN-0084-201 Version: Amendment 4 IND Number: 112.608

dose of study drug for that patient must be reported. Disease progression and death will be reported as part of the study endpoints and not as AEs or SAEs unless there is unambiguous evidence that death was due to a cause other than disease under study.

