The exploratory endpoint DCR is defined as the proportion of patients achieving a confirmed BOR of CR, PR or SD according to a) RANO criteria and b) modified RANO criteria. BOR is defined as the best response recorded from first dose (Stage 1) or randomization (Stage 2) until progressive disease , death, withdrawal of consent or end of study, whichever occurs first. To be assigned a status of CR, PR or SD, the response must be confirmed by repeat assessments that should be performed no less than 28 days after the criteria for response are first met, i.e., patients need to have two consecutive assessments of CR, PR or SD. To be assigned a BOR of SD patients must have a minimum duration of SD of at least 6 weeks.

The number and proportion of responders and non-responders based on objective response rate and DCR will be presented with 95% Clopper-Pearson Cls. Further, objective response rate and DCR will be compared between treatment arms using Fisher's exact test. The difference in the proportion of responders and corresponding 95% CI (based on the Hauck-Anderson approach) will also be displayed.

Analyses of PFS will be repeated using modified RANO criteria.

Additional exploratory analyses of the data will be conducted as deemed appropriate.

6.3.5 **Safety Analysis**

All safety analyses will be conducted in the safety population.

AEs will be coded according to the Medical Dictionary for Regulatory Activities (MedDRA). The severity of AEs will be graded according to the United States NCI CTCAE, version 4.03.

TEAEs are defined as any AE occurring or worsening on/after the first study drug dose and within 28 days after the last dose date. TEAEs leading to study drug discontinuation, TEAEs leading to dose reduction/interruption, TEAEs related to study drug, SAEs, TEAEs leading to study drug discontinuation, and TEAEs with an outcome of death will be summarized by system organ class, and preferred term. Disease progression and death will be reported as part of the study endpoints and not as AEs or SAEs. A summary of TEAEs of NCI CTCAE Grade 3 or higher, as well as the most frequent TEAEs (preferred terms) by grade, and TEAEs by relationship to study treatment, will be provided. Additionally, a summary will be done for AEs using the worst grade of the event.

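### Table 1's +/- 3-day tolerance lets the last adverse-event visit fall 25 days after the last dose and Cycle 2 Day 1 fall on Day 26, before the 28-day windows they serve have closed

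*Combined protocol and SAP*

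**What the plan says.** **The windows that are counted.** Section 3.7.1 defines a DLT as a qualifying toxicity in Cycle 1, Days 1 to 28. If none of the first three patients has one "within the DLT assessment period (Day 1 - 28), escalation will proceed to the next higher dose level". Section 5.2 has AEs reported "through and including 28 calendar days after the last administration of the investigational product". Section 6.3.5 counts as treatment-emergent any AE that occurs or worsens "on/after the first study drug dose and within 28 days after the last dose date".

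**The visits that serve them.** Section 3.7.1 states that "GDC-0084 administration will occur in 28-day cycles", so Cycle 2 Day 1 is nominally study Day 29. Table 1 gives that visit a tolerance of three days either way. The Short-Term Follow-up Visit is set at "28 days from last dose +/- 3 days". The AE row is marked for that visit but blank for the 8-weekly long-term follow-up, which collects disease status and disease-related therapies only.

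**A related instruction.** Section 4.6.7, when describing the Cycle 2 Day 1 PK sample, tells the site also to record the time of the Day 28 dose from patient information or the diary. This presumes that the Day 28 dose has already been taken.

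**The concern.** A visit that closes a counting window should not be allowed to happen before the window ends. Table 1 allows this twice.

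After treatment, a patient seen on day 25 has no later scheduled contact at which AEs are asked about, yet the treatment-emergent tables claim coverage to day 28.

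In Stage 1, Table 1 has no AE, laboratory or ECG assessment between Day 1 and Cycle 2 Day 1; the Day 2 contact is a 24-hour PK sample. A patient seen on Day 26 is next scheduled at Cycle 3 Day 1, nominally Day 57. An event on Day 27 or 28 may therefore become known late, possibly after the cohort review, for which the protocol gives no data cut-off. Some DLTs are found only by measurement, such as Grade 4 thrombocytopenia of any duration or a QTc rise. Such an event could come and go unseen.

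The error can go only one way, towards fewer DLTs (the primary endpoint) and fewer treatment-emergent AEs.

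**Working it through.** **Inputs from the protocol.** Cycle length 28 days and DLT window Days 1-28 (Section 3.7.1); tolerance of 3 days either way for both visits (Table 1); post-dose AE window 28 days (Sections 5.2 and 6.3.5).

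**Dates.**
- Cycle 2 Day 1: 1 + 28 = Day 29, the nominal date. With the tolerance, 29 - 3 = Day 26 to 29 + 3 = Day 32.
- DLT days wholly after the earliest visit: Days 27 and 28, so 2/28 = 7%, plus whatever remains of Day 26.
- Cycle 3 Day 1: 1 + 56 = Day 57, range 54 to 60.
- Short-Term Follow-up: 28 - 3 = 25 to 28 + 3 = 31 days after the last dose.
- Post-dose days after the earliest follow-up: 26, 27 and 28, so 3/28 = 11%.

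**Size for escalation (illustration).** The protocol gives no DLT rate and no onset distribution. Assume a true rate p over 28 days, onset uniform over those days, and that no event after the visit reaches the review. Under the 3 + 3 rule a level is cleared with 0 DLTs in 3 patients or 1 in 6:

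P(clear) = (1-p)^3 + 3p(1-p)^2 × (1-p)^3

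At p = 0.40: 0.216 + 0.432 × 0.216 = 0.309.

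*Every visit on Day 26.* The observable rate is p × 26/28. For p = 0.40 this is 0.3714, and P(clear) = 0.358.

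*Visits spread evenly over Days 26-32 (an assumption).* A Day 26 visit loses 2 days, a Day 27 visit loses 1, and later visits lose none. The mean loss is (2 + 1)/7 = 3/7 day, or (3/7)/28 = 1.5% of the window. The observable rate is 0.40 × (1 - 0.0153) = 0.394, and P(clear) = 0.319.

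| True DLT rate (assumed) | Full window observed | Visits spread over Days 26-32 | Every visit on Day 26 |
|---|---|---|---|
| 33% | 0.434 | 0.444 | 0.481 |
| 40% | 0.309 | 0.319 | 0.358 |

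The same worst case gives 0.906 to 0.918 at a 10% rate, 0.709 to 0.739 at 20%, and 0.172 to 0.215 at 50%. So the worst case is about 5 percentage points, and an even spread of visits gives about 1 point at the two rates shown.

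**The case against.** A reader might infer that Table 1 lets a patient be declared DLT-free on Day 26, and so materially loosens dose escalation. The documents do not support that.

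- Section 3.7.1 conditions escalation on Days 1-28, and Section 4.3.1 replaces non-safety withdrawals before the DLT period is complete so that the review has a full cohort. Clearing a patient on Day 26 would breach those rules.
- Nothing names Cycle 2 Day 1 as the visit that closes the DLT window or as the Cohort Review Committee cut-off. That role is inferred from its being the next scheduled visit. The committee's charter is not among the documents.
- Section 4.6.7 points to a visit after Day 28.
- AEs are assessed throughout the study (Section 4.6.10), later visits ask about changes since the previous one (Section 5.1), and spontaneous reports are taken (Section 5.11). A Day 27 event learned of at Cycle 3 Day 1 still has an in-window onset and still counts.
- Several DLTs depend on 7 or 14 days of persistence or non-recovery. One that starts on Day 27 cannot be settled at a Day 29 visit either.

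All of this stands, and it limits the DLT half to late knowledge and silent transient events.

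Two further safeguards are weaker than they look. Section 8 (Preparation and Administration) describes supervised dosing until Cycle 2 Day 1, but Section 4.6.7 takes the Day 28 dose time from the patient or diary, so staff contact on Day 28 is not assured. Section 4.9.1 requires laboratory tests within 48 hours before each cycle. That helps only if Cycle 2 is counted from Day 29 rather than from the early visit, and it does not cover ECGs or symptoms.

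On the post-dose half, the investigator's duty to report runs the full 28 days whatever the visit date. That duty stands, but no scheduled contact with an AE mark supports it for days 26-28.

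**Conclusion.** The point holds as a mismatch between visit tolerances and counting windows, with a small effect.

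The post-dose half is the firmer one. Up to 3 of 28 days (11%) have no scheduled AE contact at or after them, and the treatment-emergent counts for those days rest on unscheduled reports. These are secondary safety endpoints and do not bear on escalation.

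For the DLT window, up to 2 of 28 days (7%) may follow the visit, and Table 1 and Section 4.6.7 contradict each other on whether that visit can precede the Day 28 dose. The shift in clearance probability at a 40% rate is about 1 point (0.309 to 0.319) if visits spread evenly. It reaches about 5 points (0.358) only if every visit is on Day 26. Both figures also assume uniform onset and that no late event is volunteered, so they overstate the effect to the extent that patients report events. They do not show that a dose level would be wrongly cleared.

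The reason to act is that the correction is cheap, the possible error is one-directional, and two sections need reconciling in any case.

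**What to change.** In Table 1, set both visit windows to 0 to +3 days. Cycle 2 Day 1 would then fall on Days 29-32 and the Short-Term Follow-up Visit 28-31 days after the last dose. The days left after the earliest permitted visit fall from 2 to 0 in the DLT window and from 3 to 0 in the post-dose window.

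Alternatively, keep the tolerance and require a documented telephone AE check once Day 28 of Cycle 1, or day 28 after the last dose, has passed following any early visit. A call would not detect silent laboratory or ECG events, so it is the weaker option for the DLT window.

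Either way, reconcile the Cycle 2 Day 1 window in Table 1 with the Day 28 dose-time instruction in Section 4.6.7. The change concerns when assessments are made, not treatment. The cost is one table edit and slightly less scheduling flexibility, or an occasional call.
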